To demonstrate that treatment optimization, defined as prescription of treatment regimen adherent to the recommendations of the ESC guidelines will lead to clinically relevant decrease of NT-proBNP levels in	
Title: NT-proBNP levels in clinically stable patients at Visit 3
 
Title: Change of NT-proBNP levels in clinically stable CHF patients with and without treatment optimization at Visit 2
 
Description: At the Visit 3 (end of study) NT-proBNP will again be assessed in clinically stable CHF patients with baseline NT-proBNP levels ≥ 600 pg/ml. Thus, for those patients two NT-proBNP measurements will be available: at baseline and at visit 3. The individual change of NT-proBNP between both time points will be assessed in accordance to the patients' treatment history during the study, i.e. baseline HF treatment and therapeutic decision taken at Visit 2.
	Section 9.5.3

OBJECTIVE	Endpoint Title, Description and Reporting Time Frame for analysis and Unit of Measure	Stat Analysis Section
clinically stable CHF patients with baseline NT-proBNP levels \geq 600 pg/ml.	Units: Descriptive statistics for quantitative data, absolute and relative frequency distributions for treatment history subgroups Time frame: Baseline (Visit 1) and Visit 3	
To assess the baseline health-related quality of life (QoL) in CHF patients and describe the temporal course of QoL after specialist referral in clinically stable CHF patients with NT-proBNP \geq 600 pg/ml	Title: Change of EQ-5D total and individual sub-scores between Visit 3, Visit 2 and baseline Title: Change in KCCQ total and individual sub-scores between Visit 3, Visit 2 and baseline Title: Baseline EQ-5D total and individual sub-scores Title: Baseline KCCQ total and individual sub-scores Description: At baseline (all patients) and at Visit 2 and Visit 3 (only patients who have entered the prospective period of the study, i.e. clinically stable patients with a NT-proBNP level \geq 600 pg/ml) will be asked to fill out the EuroQol 5D (EQ-5D) and Kansas City Cardiomyopathy Questionnaire (KCCQ) – two quality of life (QoL) questionnaires validated for HF. Units: Mean scores, Mean change in scores/sub-scores, absolute and relative frequency distributions of QoL responders (in accordance to the patients' therapeutic regimens at baseline and after specialist referral) Time frame: Baseline (Visit 1) and Visit 2 and Visit 3	Section 9.5.1

3 Investigational plan

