6.6.2 Patient Reported Outcomes (PRO)

The impact of the disease per se (in all patients) and of CHF treatment optimization (in patients in the prospective period) on health related quality of life (QoL) will be assessed by the following measures:

- EuroQol EQ-5D (EQ-5D-5L)
- Kansas City Cardiomyopathy Questionnaire (KCCQ)

Both questionnaires are available as validated translations in local language.

The patient should be given sufficient instruction, space, time and privacy to complete the questionnaire. The study coordinator should check the responses to the questionnaire for completeness and encourage the patient to complete any missing responses.

As treatment optimization can affect all derived scores and subscales of both questionnaires, the change from baseline for all measures and scales derived from both questionnaires will be analyzed for patients who enter the prospective period of the study.

For patients who are not clinically stable or show NT-proBNP levels < 600 pg/ml only the baseline QoL will be documented.

The patients' responses shall be entered into the CRF by the investigator. The original questionnaire will be kept with the patient's file as the source document.

Completed questionnaires will be reviewed and examined by the investigator, before the clinical examination, for responses that may indicate potential adverse events (AEs) or serious adverse events (SAEs). The investigator should review not only the responses to the questions in the questionnaires but also for any unsolicited comments written by the patient. If AEs or

[figure not shown]
SAEs are confirmed, then the physician must record the events as per instructions given in [Section 7.1](#) and [Section 7.2](#) of the protocol.

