9.5.1 Patient reported outcomes

Health related quality of life as measured by the patient reported outcomes EQ-5D-5L and KCCQ.

The KCCQ instrument includes several domains. Only the domains that address HF symptoms and physical limitations will be analyzed. The clinical summary score of KCCQ is computed as the mean of the following available domain scores:

- Physical limitation score
- Total HF symptom score

Minimal clinical improvement according to the KCCQ will be defined for each of the two domain scores as an improvement of at least 5 points compared to baseline ([Flynn, Lin et al. 2012](#)).

The EQ-5D-5L consists of five domains and one visual analogue scale. This instrument assesses morbidity, self-care, usual activity, pain, and anxiety and depression of patients on a five-point rating scale ranging from *1=no problems* to *5=extreme problems*. A continuous utility index will be derived from these dimensions.

Quantitative outcomes such as KCCQ sub-domains, EQ-5D visual analogue scale and EQ-5D utility index will be displayed in terms of descriptive statistical parameters such as valid n, mean, SD, minimum, median and maximum at each visit.

Furthermore, for visit 2 the change from baseline and for visit 3 the change from baseline and from visit 2 will be calculated and displayed.

In case of ordinal or dichotomous measures such as EQ-5D dimensions and KCCQ response distributions in terms of absolute and relative frequencies will be provided for the single visits.

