4.2 Study population

According to the protocol, it was planned to enroll a total of 4000 CHF patients of which approximately 2400 are estimated to enter the prospective period (who are considered clinically stable and show NT-proBNP levels ≥ 600 pg/ml). The recruitment was to be regarded as completed once approximately 2400 patients have entered the prospective period irrespectively how many patients have been enrolled totally.

However, it was decided by Novartis to determine the study prematurely, i.e. to stop recruiting and data collection in March 2018: therefore, last patient first visit was on 07 March 2018, last patient last visit on 23 March 2018. This means, that not every subject was able to perform Visit 3 of the study.

Patients/subjects eligible for inclusion in this study had to fulfil all of the following criteria:

- Willing and able to provide written informed consent and accept study procedures and time schedule.

- Age \geq 18 years.
- Patients suffering from chronic heart failure (the heart failure diagnosis must have been made or confirmed by a cardiologist and/or hospital physician at any time in the patient's medical history).
- Patients with reduced ejection fraction ($\leq 40\%$) as confirmed at any time point in the patient's medical history.

Patients/subjects fulfilling any of the following criteria were not eligible for inclusion in this study.

- Use of investigational drugs either within 5 half-lives of enrollment, or within 30 days, or until the expected pharmacodynamic effect has returned to Baseline, whichever is longer.
- Major surgery in the last 3 months prior to Baseline or planned major surgery or cardiac intervention during the study.
- Cancer or other significant co-morbidities implying that the patient's condition is unstable.
- Comorbidities that can be associated with elevated natriuretic peptide (NP) levels: renal insufficiency (eGFR < 30 ml/min/1.73 m² calculated according to MDRD formula), recent (less than 3 months) cerebral trauma or recent (less than 3 months) cerebrovascular incident, novel diagnosis or acute exacerbation of COPD within the last 3 months.
- Patients who are primarily managed and regularly followed-up by a cardiologist for their HF
- Highly frail patients whose estimated lifespan due to comorbidities by the judgement of the investigator is less than 6 months.

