- Acceptance of cardiologist's advice on patient level (All changes implemented, No changes implemented, Changes partially implemented).
- Reason for non-acceptance of the cardiologist's advice

Patient reported outcomes

- EQ-5D VAS at Visit 1, Visit 2, Visit 3, absolute change from Baseline to Visit 2 and Visit 3 and absolute change from Visit 2 to Visit 3 (change calculated via *post minus pre value*).
- EQ-5D utility index at Visit 1, Visit 2, Visit 3, absolute change from Baseline to Visit 2 and Visit 3 and absolute change from Visit 2 to Visit 3 (change calculated via *post minus pre value*).
- EQ-5D single dimensions at Visit 1, Visit 2 and Visit 3.
- KCCQ sub-scores, total symptom score and clinical summary score at Visit 1, Visit 2, Visit 3, absolute change from Baseline to Visit 2 and Visit 3 and absolute change from Visit 2 at Visit 3 (change calculated via *post minus pre value*).

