7.7 Patient reported outcomes

Patient reported outcomes as described in [Section 6.2](#) will be analysed at Visit 1 for the Enrolled Set and at Visit 1, Visit 2 and Visit 3 for the Follow-up Set following the procedures described in [Section 7.1](#).

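### The five EQ-5D dimensions are tabulated only visit by visit, although Protocol Table 2-1 and 6.6.2 ask for change; the conflict starts inside the protocol and the SAP inherits it

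*SAP*

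**What the plan says.** Three places in the protocol bear on the EQ-5D dimensions.

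- Table 2-1 (Protocol 2.4) titles a secondary endpoint "Change of EQ-5D total and individual sub-scores between Visit 3, Visit 2 and baseline". Its units column includes mean change in scores and sub-scores, and it refers to Section 9.5.1 for the analysis.
- Protocol 6.6.2 says that "the change from baseline for all measures and scales derived from both questionnaires will be analyzed for patients who enter the prospective period".
- Protocol 9.5.1 plans change for quantitative outcomes, naming the KCCQ sub-domains, the VAS and the utility index. For ordinal measures it says that "EQ-5D dimensions and KCCQ response distributions in terms of absolute and relative frequencies will be provided for the single visits".

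SAP 6.2 follows 9.5.1. Its entry for the utility index begins "EQ-5D utility index at Visit 1, Visit 2, Visit 3, absolute change from Baseline to Visit 2 and Visit 3 and absolute change from Visit" and closes with the interval between the second and third visits; the VAS and KCCQ scores are treated the same way. The dimensions get only "EQ-5D single dimensions at Visit 1, Visit 2 and Visit 3". SAP 7.7 adds that patient-reported outcomes "will be analysed at Visit 1 for the Enrolled Set and at Visit 1, Visit 2 and Visit 3 for the Follow-up Set", using the general methods of SAP 7.1. Those give frequency distributions for qualitative data, with percentages that leave out patients with missing values. No shift table or improved/worsened count is planned.

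On the early stop, SAP 4.2 states: "This means, that not every subject was able to perform Visit 3 of the study".

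**The concern.** The secondary objective is to describe how quality of life develops after referral. A set of visit-wise percentages answers a different question from change within patients. If a dimension looks the same at two visits, the table cannot distinguish a population in which nobody moved from one in which many improved and as many worsened.

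The second issue is the denominator. Within the Follow-up Set, patients with Visit 3 data are essentially a subset of those with Visit 1 data. If the patients who never reached Visit 3 had more problems at Visit 1, the Visit 3 column looks better with no patient having improved; if they had fewer, it looks worse. A reader who takes the columns as a time course could credit or blame the referral for a change in case mix.

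**Working it through.** The plan states no figure on this point, so there is nothing to reproduce. The check is a comparison of texts followed by an identity.

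**Who can lack Visit 3.** SAP 4.2 puts the last first visit on 07 March 2018 and the last visit of any patient on 23 March 2018, 16 days later. SAP 4.4 places Visit 3 no earlier than 3 months after Visit 2. A patient whose Visit 2 fell after about 23 December 2017 could therefore not reach Visit 3 at that minimum. Missing Visit 3 thus depends at least partly on entry date and time to referral. Protocol 3.1 says referral policies differ between countries, so case mix could differ between patients with and without Visit 3. The documents do not show that it does, and give no count of patients without Visit 3.

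**What marginal frequencies leave open.** Suppose 50% report no problems in a dimension at both visits, in the same patients. The share moving into that level can be anything from 0% to 50%, offset by an equal share leaving it. The two columns are identical throughout.

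**Size of the denominator effect.** Let m be the fraction of the Follow-up Set without Visit 3, and let p_c and p_n be the Visit 1 percentages with no problems among patients later seen and not seen. Assume no patient changes.

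- Visit 1 column: (1 − m) × p_c + m × p_n
- Visit 3 column: p_c
- Difference, Visit 3 minus Visit 1: m × (p_c − p_n)

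Example with assumed inputs: m = 30%, p_c = 50%, p_n = 40%. Visit 1 shows 0.7 × 50 + 0.3 × 40 = 47%; Visit 3 shows 50%. The apparent gain is 3 points, and the paired change is 0.

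Apparent shift in percentage points, all inputs assumed:

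| m | gap 0 | gap 5 | gap 10 | gap 20 |
|---|---|---|---|---|
| 10% | 0 | 0.5 | 1 | 2 |
| 20% | 0 | 1 | 2 | 4 |
| 30% | 0 | 1.5 | 3 | 6 |
| 40% | 0 | 2 | 4 | 8 |
| 50% | 0 | 2.5 | 5 | 10 |

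A gap of 30 points with m = 40% would give 0.4 × 30 = 12. The sign reverses if the patients not seen were the healthier ones.

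**Does the utility index cover the gap?** Only in aggregate. In SAP 4.5.2 a slight mobility problem and a slight usual-activities problem both weigh 0.051. A patient who loses the first and gains the second has an index change of −0.9675 × (−0.051 + 0.051) = 0, although two dimensions moved.

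**The case against.** The strongest reply is that the SAP carries out the analysis the protocol specifies. Table 2-1 sends this endpoint to 9.5.1, and 9.5.1 separates quantitative outcomes, which get change, from the ordinal dimensions, which get frequencies at single visits. This stands. A reader might infer that the SAP departed from the protocol and failed to declare it in SAP 7.13. The documents do not support that: the SAP matches the protocol's analysis section, and the conflict lies between that section and Table 2-1 with 6.6.2.

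Second, the individual sub-scores need not mean the five dimensions. Mean change suits a quantitative score better than a five-level item, and the dimensions are answered directly rather than derived. This stands in part. However, the documents name no other EQ-5D sub-scores, and 6.6.2 is worded to cover everything from both questionnaires, so the five-dimension reading remains the natural one.

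Third, the course of quality of life is already described with paired data: SAP 6.2 plans change over all three intervals for the utility index, VAS and KCCQ scores, and SAP 7.10 requires both values for a change from baseline. This stands and limits the point to the dimension-level picture.

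Fourth, an administrative cut-off gives no particular reason to expect a large health difference between patients with and without Visit 3, and the absolute frequencies let a reader see n fall. Also fair. A falling n, however, does not show whether the remaining patients differed at Visit 1.

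**Conclusion.** The point holds in a limited form. Table 2-1 and 6.6.2, read naturally, call for change in the EQ-5D dimensions; Protocol 9.5.1 and SAP 6.2 and 7.7 deliver only observed-case frequencies by visit. Those cannot give the number who improved or worsened, whatever the pattern of missing data. A difference between the Visit 1 and Visit 3 columns can also partly reflect who was seen, by m × (p_c − p_n). That is 0 to 10 points over the assumed ranges, and exactly zero if patients without Visit 3 resemble those with it at Visit 1.

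A reader might go further and conclude that any shift in these tables is an artefact, or that the quality-of-life objective is not met. Neither follows. Both inputs to the identity are unknown, and paired change is planned for every other EQ-5D and KCCQ score. This is a modest gap in a descriptive secondary outcome.

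**What to change.** In SAP 6.2 and 7.7, or in an addendum as SAP 7.12 allows, add for each EQ-5D dimension, among Follow-up Set patients with both assessments: the paired n and the number and percentage improved, unchanged and worsened in level, for Visit 1 to 2, Visit 1 to 3 and Visit 2 to 3. Keep the visit-wise frequencies as supporting tables. Full 5 x 5 shift tables are optional: five dimensions over three intervals would make fifteen, more than the question needs. Reconcile Protocol 9.5.1 with Table 2-1 and 6.6.2, stating whether the individual sub-scores include the five dimensions.

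The cost is a few descriptive tables from data already collected, repeated for the separate Belgian analysis (SAP 7.11 and 7.12). The paired counts remove the change-of-patients effect but describe only patients seen at both visits. Carrying them over to patients without Visit 3 would still be an assumption, which the report should state.

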6.4 Safety variables

Vital signs

- Body Mass Index (BMI), defined as $Weight \text{ (in kg)}/(Height \text{ (in m)})^2$, at Visit 1 and Visit 3
- Mean systolic blood pressure (in mmHg) at Visit 1, Visit 2 and Visit 3
- Mean diastolic blood pressure (in mmHg) at Visit 1, Visit 2 and Visit 3
- Pulse (in bpm) at Visit 1, Visit 2 and Visit 3

Signs and symptoms of HF including NYHA

- NYHA functional class (Class I to Class IV) at Visit 1, Visit 2 and Visit 3
- Existence of signs and symptoms of HF at Visit 1: Dyspnea at rest, Dyspnea upon effort, Paroxysmal nocturnal dyspnea, Fatigue, Chest pain / discomfort, Anxiety, Palpitations at rest, Palpitation on exertion, Orthopnea, Rales, Peripheral edema, Other (Absent, Present)
- Existence of signs and symptoms of HF at Visit 2 and Visit 3: Dyspnea at rest, Dyspnea upon effort, Paroxysmal nocturnal dyspnea, Fatigue, Chest pain / discomfort, Anxiety, Palpitations at rest, Palpitation on exertion, Orthopnea, Rales, Peripheral edema, Other (Absent, Worsened, Newly developed, Improved, No change)

Laboratory assessments others than NT-proBNP

- Assessment of Potassium, Haemoglobin, Serum creatinine at Visit 1, Visit 2 and Visit 3 (Normal value – not clinically significant, Abnormal value – not clinically significant, Abnormal value – clinically significant)
- Glomerular filtration rate (GFR) in ml/min according to Cockroft-Gault at Visit 1, Visit 2 and Visit 3.
- GFR in ml/min according to MDRD at Visit 1, Visit 2 and Visit 3.

Adverse events

- AE term (system organ class [SOC] and preferred term [PT])
- Serious AE (SOC and PT)
- AE related to study procedure (SOC and PT)
- Fatal AE (SOC and PT)

6.5 Other variables

General data

- Country
- Subject ID
- Study participation according to protocol (Yes, No)
- Reason for premature discontinuation
- Time between Visit 1 and Visit 2 (in days)
- Time between Visit 2 and Visit 3 (in days)

Inclusion criteria

Inclusion criteria as defined in Section 4.2.

Exclusion criteria

Exclusion criteria as defined in Section 4.2.

Protocol deviations

- Protocol deviation code

Non-HF medication

- Prior Non-HF medication (ATC level 2 and preferred name)
- Concomitant Non-HF medication (ATC level 2 and preferred name)
- Reason for Non-HF medication

7 Statistical methodology

7.1 General methodology

In general, descriptive statistical analyses will be performed. If not described differently, analyses at Baseline will be performed for all patients in the Enrolled Set and additionally stratified by inclusion into the prospective period of the study (Yes, No). Analyses regarding the prospective period of the study will be carried out in the Follow-up Set. In specific cases, analysis in the Follow-up Set will be additionally stratified by adherence to ESC guidelines before and after referral to cardiologist (ESC non-conform/ESC conform, ESC non-conform/ESC non-conform, ESC conform/ESC conform, ESC conform/ESC non-conform, details are specified below). All subgroup analyses are described below in [Section 7.10](#).

Quantitative data (e.g. age) will be analysed by the statistical parameters valid N, missing N, mean, standard deviation, minimum (0%), median (50%), and maximum (100%).

Qualitative data (e.g. gender) will be presented by means of (absolute and relative) frequency distributions. The calculation of percentages will be based on the observed data per parameter, excluding patients with missing values (exceptions are described below). Exact Clopper-Pearson 95%-confidence intervals (CIs) will be calculated if applicable (see descriptions below).

Analyses of conditional endpoints (e.g. amount of cigarettes consumption in pack years) will be based on the number of subjects fulfilling the respective condition (e.g. patients with current or former consumption of cigarettes).

If indicated by the data, results of statistical analysis may be complemented by individual patient listings.

7.2 Disposition of patients

Analysis of patient dispositions will be performed without stratifications described in [Section 7.1](#).

The following variables will be analysed in terms of frequency distributions describing the disposition of patients in this study:

- Number of patients in the analysis sets overall and by country (all patients)

- Protocol deviations (Enrolled Set and Follow-up Set)
- Number of patients violating inclusion and exclusion criteria (for each criterion; Enrolled Set, Follow-up Set)
- Number of patients with premature study discontinuation (Follow-up Set)
- Reasons for premature study discontinuation overall (patients with preliminary study discontinuation)

In addition, the variables at Visit 1 for *NT-proBNP, stability and suitability for prospective interventional period* (as described in [Section 6.2](#)) will be summarised without further stratification as follows:

- NT-proBNP ever tested before Visit 1 (Enrolled Set)
- NT-proBNP in groups (< 600 pg/ml, \geq 600 pg/ml) at Visit 1 (Enrolled Set)
- Clinical stability of the patient (Enrolled Set)
- Suitability for prospective interventional period of the study (Enrolled Set)
- Referral to cardiologist (Enrolled Set – patients suitable for prospective period)

The reasons for non-referral to cardiologist will be listed by patient.

The time between Visit 1 and Visit 2 and the time between Visit 2 and Visit 3 will be summarized for the Follow-Up Set.

7.3 Description of Baseline status

The analysis of the Baseline status of the patients will be performed in the Enrolled Set (stratified by inclusion in the prospective period of the study). Summary statistics will be provided for the variables described in [Section 6.2](#) in the sub-section *Demographics*.

The following definitions will be applied for derived variables:

- Age will be calculated as *(date of visit 1 – 1 July in year of birth)/365.25*.
- General smoking status will be classified as follows:
 - Never: “did the patient ever or does the patient currently smoke/consume tobacco” is answered with “No”
 - Current: “did the patient ever or does the patient currently smoke/consume tobacco” is answered with “Yes” **and** consumption of at least one tobacco product answered with “Current”
 - Former: “did the patient ever or does the patient currently smoke/consume tobacco” is answered with “Yes” **and** consumption of at least one tobacco product answered with “Former” **and** consumption of no tobacco product answered with “Current”
 - For patients where “did the patient ever or does the patient currently smoke/consume tobacco” is answered with “Yes” **and** consumption of all tobacco product answered with “Never” or not specified, the smoking status remains missing

- Consumption of single tobacco products: Patients where “did the patient ever or does the patient currently smoke/consume tobacco” is answered with “No” will be assigned to “Never”.
- If smoking status of cigarettes is “Former” or “Current”, the amount of consumption in pack years will be displayed. Pack years will be calculated as *estimated amount consumed on average per day (in packs) x total duration of consumption (in years)*. The number of packs per day will be estimated as *number of cigarettes per day / 20*. If the duration of consumption is not given in years, it will be transformed accordingly.
- For all other tobacco products, the duration of consumption in years will be provided for patients with consumption status “Former” or “Current”. If the duration of consumption is not given in years, it will be transformed accordingly.

For variables with category “Other”, any specifications reported will be listed.

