To assess in clinically stable patients the impact of patients' key baseline characteristics on the cardiologists' and primary care physicians' prescription practice for HF treatment and the adherence of these treatment choices to the recommendations of the current ESC guidelines.	
Title: Proportion of clinically stable patients for whom the cardiologist and/or primary care physician optimizes treatment (i.e. prescribes a treatment regimen adherent to ESC guideline recommendations) post referral, stratified according to key baseline characteristics
 
Description: For patients who enter the prospective period of the study the post-referral treatment choice of cardiologists and/or primary care physicians will be documented; for patients, for whom the cardiologist and/or primary care physician chose to prescribe a novel HF treatment, the treatment will be assessed, if it fulfills the definition of adherent to ESC guideline recommendation. The proportion of patients for whom an ESC guideline adherent treatment was de novo prescribed will be assessed stratified according to anamnestic (e.g. duration of HF, previous treatment of HF, presence of cardiovascular/ metabolic/ pulmonary comorbidities), demographic (e.g. sex, race, smoking status) and NT-proBNP level categories (e.g. 600 -799 pg/ml, 800 – 999 pg/ml, 1000 – 1200 pg/ml, > 1200 pg/ml).
 
Units: Absolute and relative frequency distributions.
 
Time frame: Visit 2 and Visit 3
	Section 9.3
To describe the blood levels of NT-proBNP in CHF patients managed in the primary care setting	
Title: NT-proBNP
 
Description: NT-proBNP levels (pg/ml) will be measured at baseline in all consecutive patients who satisfy the inclusion and exclusion criteria. Measurements are performed on-site by means of a handheld device provided for the purposes of the study.
 
Units: Descriptive statistics for quantitative data, absolute and relative frequency distributions in clinically stable and unstable CHF patients
	Section 9.5.3

OBJECTIVE	Endpoint Title, Description and Reporting Time Frame for analysis and Unit of Measure	Stat Analysis Section
	Time frame: One measurement in all consecutive patients at baseline (Visit 1)	

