6.2 Variables with respect to the secondary objectives

Demographics

- Age (in years)
- Age in groups (< 65, ≥ 65 to < 75, ≥ 75 to < 85, ≥ 85 years)
- Gender (Male, Female)
- Race (Caucasian, Black, Asian, Other). If "Other": Specification
- Living characteristics (Living independently in household (alone), Living independently in household (with spouse or significant other), Living in residence with family member (non-spousal or significant other), Living in a long term care facility, Transient housing)
- Environmental living situation (Urban, Suburban, Rural)
- Health insurance status (Statutory health insurance, Private health insurance, Combination of statutory and private health insurance, None)
- Highest educational level (Primary education, Secondary education, University, None)
- Employment status (Student, Employed (part time), Employed (full time), Homemaker, Retired, Unemployed, Sustained sick leave)
- General smoking status (Never, Former, Current)
- Consumption of cigarettes (Never, Former, Current).
 - If "Former" or "Current": amount of consumption in pack years.
- Consumption of electronic cigarettes (Never, Former, Current).
 - If "Former or Current": Duration of consumption (in years).
- Consumption of cigars (Never, Former, Current)
 - If "Former or Current": Duration of consumption (in years).

- Consumption of pipes (Never, Former, Current).
 - If “Former or Current”: Duration of consumption (in years).
- Consumption of chewing tobacco (Never, Former, Current).
 - If “Former or Current”: Duration of consumption (in years).
- Consumption of nicotine patches (Never, Former, Current).
 - If “Former or Current”: Duration of consumption (in years).
- Consumption of other tobacco products (Never, Former, Current).

Clinical features (Visit 1)

- Primary etiology of HF (Ischemic, Non-Ischemic).
- Primary etiology of HF if “Non-Ischemic” (Hypertensive, Diabetic, Alcoholic, Viral cardiomyopathy, Infectious cardiomyopathy, Peripartum, Drug induced, Cardiac arrhythmia, Valvular disease, Other). If “Other”: Specification
- Duration of HF (in years)
- Duration of HF in categories (> 3 years, ≤ 3 years).
- Any hospitalization due to HF in the last 12 months (Yes, No)
- Any visit of emergency room (without hospitalization) due to HF in the last 12 months (Yes, No)
- Any visit of an HF outpatient clinic or a cardiologist due to HF in the last 12 months (Yes, No)

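### As worded, SAP 7.3 appears to count nicotine patches as a tobacco product, so an ex-smoker on a patch would be reported as a current smoker at baseline

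*SAP*

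**What the plan says.** SAP 6.2 (Demographics) has one summary variable, general smoking status, followed by a Never/Former/Current item for each of cigarettes, electronic cigarettes, cigars, pipes, chewing tobacco, nicotine patches and a remainder category. The patch item reads "Consumption of nicotine patches (Never, Former, Current" and carries a duration in years for former or current users. The next item reads "Consumption of other tobacco products (Never, Former, Current".

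SAP 7.3 derives the summary variable in three steps.

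- Never: the lead question, "did the patient ever or does the patient currently smoke/consume tobacco", is answered No.
- Current: the lead question is Yes and "consumption of at least one tobacco product answered with" Current.
- Former: the lead question is Yes, at least one product is Former, and "consumption of no tobacco product answered with" Current.

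If the lead question is Yes but every product is Never or blank, status stays missing. For items other than cigarettes, 7.3 says: "For all other tobacco products, the duration of consumption in years will be provided". No sentence in either section removes patches from the products counted.

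**The concern.** A nicotine patch is commonly used by people who are stopping or have stopped smoking. If it counts as a tobacco product, the patients most clearly marked as having quit are placed in the group the variable is meant to separate them from.

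What is at stake is the accuracy of a descriptive result. Describing baseline demographics is the first secondary objective (Protocol 2.2), and Protocol Table 2-1 names smoking status in its Demographics endpoint. SAP 7.3 tabulates it in the Enrolled Set, stratified by inclusion in the prospective period. General smoking status is the single line that summarises all the products. SAP 2.5 makes the methods in the SAP binding for statistical programming, so the literal wording matters.

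**Working it through.** The plan gives no figure to reproduce. The check is whether the SAP's wording includes patches, and what the rule then does.

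**Are patches included?** Three places bear on it.

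1. SAP 6.2 puts patches immediately before an item for *other* tobacco products. The word 'other' implies that the items above it are tobacco products too.
2. SAP 6.2 gives patches a duration. The only rule in SAP 7.3 that provides durations for items other than cigarettes calls those items tobacco products: "For all other tobacco products, the duration of consumption in years will be provided for patients with consumption status" Former or Current.
3. SAP 7.3 sets single tobacco products to Never when the lead question is No. If patches were not among them, 7.3 would contain no handling rule for the patch item.

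All three point to inclusion, though none is a definition.

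**What does the rule do?** Items not mentioned are Never.

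| Lead question | Cigarettes | Patches | Status with patches counted | Status without patches |
|---|---|---|---|---|
| Yes | Former | Current | Current | Former |
| Yes | Current | Current | Current | Current |
| Yes | Former | Former | Former | Former |
| Yes | Never | Current | Current | missing |
| Yes | Never | Former | Former | missing |
| No | any | any | Never | Never |

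The first row is the problem. The Current condition is met by the patch item alone, and the Former condition fails for the same reason. No row loses a Current classification because patches are counted, so the number classed as Current can only go up.

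**Size.** Let n be the patients with non-missing status, c those Current on some other product, and k those in the first row. These k patients have a status either way, so n does not change. The reported share is (c + k)/n instead of c/n, an excess of k/n. The documents give neither k nor n. The fourth and fifth rows do change the denominator, because SAP 7.1 leaves missing values out of percentages.

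**Where is the variable used?** SAP 7.4.2 (primary analysis) and SAP 4.5.1 (adherence definition) do not use it. The SAP 7.11 subgroups are gender, age group, HF duration, NT-proBNP category and country cluster; smoking is not among them.

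**The case against.** The strongest reply is that the misclassification is an inference. SAP 7.3 refers to tobacco products, not to every listed item, and the lead question asks about tobacco. No sentence calls a patch a tobacco product, and a programmer could take the term literally and leave it out. The duration sentence is also loose evidence: it promises a duration for all other tobacco products, yet the remainder item in 6.2 has none. This stands in part. The term is undefined, and the conclusion is conditional on the more natural reading. But two programmers could then produce different tables from the same SAP, which also calls for a definition.

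The second reply is that the product rows already show the facts. Cigarettes, patches and the rest are each reported as Never/Former/Current, with pack-years for cigarettes. This is correct, and it limits the harm to the summary line. It does not correct that line.

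The third is that the variable already pools smoked and unsmoked products, so including patches is a labelling choice. Chewing tobacco is still tobacco use, whereas a patch can mark having stopped.

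A reader might also infer that the adherence results by smoking status would be distorted, because Protocol Table 2-1 gives "demographic (e.g. sex, race, smoking status" among its stratification examples. The documents do not support that. The protocol offers it only as an example, and the SAP does not carry smoking status into its subgroup list.

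**Conclusion.** The point holds as a minor one. On the SAP's own wording, an ex-smoker currently using a patch is classed as Current, and the count of current smokers can only be overstated. This rests on reading patches as one of the tobacco products, which the text favours but does not state.

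The effect is confined to one descriptive baseline variable. No estimate, interval or subgroup result in the SAP depends on it.

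A reader might want to attach a count, for example by taking an assumed share of patch users from the 4,000 planned patients. The documents do not support one. They give no patch use and no smoking prevalence, and SAP 4.2 records that recruitment and data collection were stopped early, so 4,000 is not a safe base. The most that can be said is that the excess share equals the proportion of patients in the first row of the table.

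**What to change.** In SAP 7.3, list the SAP 6.2 items that count towards general smoking status: cigarettes, electronic cigarettes, cigars, pipes, chewing tobacco and other tobacco products. State that nicotine patches do not count. An explicit list also settles the same question for electronic cigarettes. Patch use stays in its own row, which is already planned.

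The cost is one line of text and one line in the derivation program. No new data are needed, because patches are recorded as a separate item.

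There is one small downside. A patient whose lead question is Yes and who has only patches marked would have missing status under the existing 7.3 rule, and would drop out of the percentages under SAP 7.1. Report the number of such patients beside the table.
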